5.6.3.2. Vital Signs

Continuous vital sign parameters including pulse, blood pressure (systolic and diastolic) will be summarized at each assessment time point. Change from baseline by study and study periods as specified in Section 5.6 will be summarized. Descriptive statistics (mean, standard deviation, median, minimum and maximum) will be presented.

Incidence of treatment-emergent abnormal vital signs during intervention, as defined in Table 6, will be summarized for participants who had a baseline assessment and at least 1 postbaseline assessment for that vital sign.

Table 6: Clinically Important/Markedly Abnormal Vital Signs

Vital Sign	Criteria
Pulse	$>[120]$ bpm and with $>[30]$ bpm increase from baseline
	$<[50]$ bpm and with $>[20]$ bpm decrease from baseline
Systolic blood pressure	$>[180]$ mm Hg and with $>[40]$ mm Hg increase from baseline
	$<[90]$ mm Hg and with $>[30]$ mm Hg decrease from baseline
Diastolic blood pressure	$>[105]$ mm Hg and with $>[30]$ mm Hg increase from baseline
	$<[50]$ mm Hg and with $>[20]$ mm Hg decrease from baseline
Respiratory rate	$>[20]$ breaths per minute

5.6.3.3. Columbia-Suicide Severity Rating Scale

The C-SSRS will be used as a screening tool to prospectively evaluate suicidal ideation and behavior among study participants. The C-SSRS measures 5 possible levels of suicidal ideation and 4 possible suicidal behaviors, as well as non-suicidal self-injurious behavior. The assessment is a fully-structured, participant self-report C-SSRS questionnaire, including standardized questions, follow-up prompts, error handling routines, and scoring conventions. Two versions of the C-SSRS will be used in this study, the *Lifetime* version and the *Since Last Contact* version. The *Lifetime* version will be conducted during the screening visit and the *Since Last Contact* version will be conducted at all other visits.

At the screening visit, the C-SSRS should be completed as the first assessment after signing informed consent and before any other tests, procedures, or other consultations. For subsequent visits, the C-SSRS should be completed after all PROs and before any other tests, procedures, or

other consultations. Participants will be interviewed by the investigator or trained study site personnel in a private, quiet place.

The following are C-SSRS categories and have binary responses (yes/no). A “yes” response to any C-SSRS category will be assigned a score as below:

Suicidal Ideation (1-5)

1 = Wish to be Dead

2 = Non-specific Active Suicidal Thoughts

3 = Active Suicidal Ideation with Any Methods (Not Plan) without Intent to Act

4 = Active Suicidal Ideation with Some Intent to Act, without Specific Plan

5 = Active Suicidal Ideation with Specific Plan and Intent

Suicidal Behavior (6-10)

6 = Preparatory Acts or Behavior

7 = Aborted Attempt

8 = Interrupted Attempt

9 = Actual Attempt (non-fatal)

10 = Completed Suicide

If no events qualify for a score of 1 to 10, a score of 0 will be assigned (0 = “Negative result [no suicidal ideation or behavior]”). Higher scores indicate greater severity.

Suicidal ideation and behavior will be summarized based on the most severe/maximum post baseline C-SSRS outcome or AE of suicidal ideation, suicidal behavior excluding completed suicide, or completed suicide through Week 16 for 77242113PSO2001 study or through Week 56 (Week 40 of the 77242113PSO2002 study), and from Week 16 (Week 0 of the 77242113PSO2002) through Week 56 (Week 40 of the 77242113PSO2002 study) for participants in the 77242113PSO2002 study period. In addition, frequency distribution of the most severe/maximum post baseline C-SSRS outcome will be tabulated by C-SSRS categories and intervention group through Week 16 and through Week 56. The baseline is defined as the most severe/maximum C-SSRS score at either screening or Week 0.

The maximum score assigned for each participant will also be summarized into one of three broad categories: No suicidal ideation or behavior, suicidal ideation, suicidal behavior. A shift table for change in C-SSRS categories of no suicidal ideation or behavior, suicidal ideation, and suicidal behavior from baseline through Week 16 for study 77242113PSO2001 and through 56 for the

combined 77242113PSO2001 and 77242113PSO2002 studies, and from Week 16 through Week 56 for participants in the 77242113PSO2002 study period will be presented, where the baseline category is based on C-SSRS score form study 77242113PSO2001 and the post baseline is based on C-SSRS or AE data.

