19. Has suicidal ideation or suicidal behavior in the last 6 months that may be defined as a Columbia-Suicide Severity Rating Scale (C-SSRS) rating at screening of: Suicidal Ideation with Intention to Act (“Ideation level 4”), Suicidal Ideation with Specific Plan and Intent (“Ideation level 5”), or suicidal behavior (actual suicide attempt, interrupted suicide attempt, aborted suicide attempt, or preparatory behaviors for making a suicide attempt), and is considered to be at risk by the investigator based on an evaluation by a mental health professional. In addition, participants with C-SSRS ratings of Wish to be Dead (“Ideation level 1”), Non-Specific Active Suicidal Thoughts (“Ideation level 2”), Active Suicidal Ideation with Any Methods (Not Plan) without Intent to Act (“Ideation level 3”) or non-suicidal self-injurious behavior who are determined to be at risk by the investigator may not be randomized.

Infections or Predisposition to Infections

20. Has a history of chronic or recurrent infectious disease, including but not limited to chronic renal infection, chronic chest infection (eg, bronchiectasis), recurrent urinary tract infection (recurrent pyelonephritis or chronic nonremitting cystitis), fungal infection (mucocutaneous candidiasis), or open, draining, or infected skin wounds or ulcers.
21. Has a history of an infected joint prosthesis or has received antibiotics for a suspected infection of a joint prosthesis, if that prosthesis has not been removed or replaced.
22. Has had a serious infection (eg, sepsis, pneumonia, or pyelonephritis), or has been hospitalized or received IV antibiotics for an infection during the 2 months before screening.

23. Has or has had herpes zoster within the 2 months before screening.
24. Has a history of active granulomatous infection, including histoplasmosis or coccidioidomycosis, before screening. Refer to Exclusion Criterion 32 for information regarding eligibility with a history of latent TB.
25. Has a chest radiograph within 3 months before the first administration of study intervention that shows an abnormality suggestive of a malignancy or current active infection, including TB.
26. Has ever had a nontuberculous mycobacterial infection or opportunistic infection (eg, cytomegalovirus, pneumocystis, or aspergillosis).
27. Tests positive for hepatitis B virus (HBV) infection (Section 10.10) or who are seropositive for antibodies to hepatitis C virus (HCV) at screening.

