10.7. Appendix 7: Columbia Suicide Severity Rating Scale

Appendix 7a: Columbia Suicide Severity Rating Scale – Baseline-screening (Past x months = Past 6 months)

SUICIDAL IDEATION											

Ask questions 1 and 2. If both are negative, proceed to the "Suicidal Behaviour" section. If the answer to question 2 is "yes", ask questions 3, 4 and 5. If the answer to question 1 and/or 2 is "yes", complete the "Intensity of Ideation" section below.
 
1. Wish to be Dead Subject endorses thoughts about a wish to be dead or not alive anymore, or a wish to fall asleep and not wake up. Have you wished you were dead or wished you could go to sleep and not wake up?
 
If yes, describe:
		Lifetime: Time He/She Felt Most Suicidal 
 
 Yes	No	Yes	No	
 
 				
 
	Yes	No	Yes	No					
Yes	No	Yes	No								
											

2. Non-Specific Active Suicidal Thoughts General non-specific thoughts of wanting to end one's life / commit suicide (e.g. "I've thought about killing myself") without thoughts of ways to kill oneself / associated methods, intent, or plan during the assessment period. Have you actually had any thoughts of killing yourself?
 
If yes, describe:
		
 
 Yes	No	Yes	No	
 
 				
 
	Yes	No	Yes	No					
Yes	No	Yes	No								
											

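### The C-SSRS shift tables take their baseline from a screening score with no recall window, so on-study ideation after a remote history cannot register as worsening

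*SAP*

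**What the plan says.** SAP Section 5.6.3.3 describes the screening instrument thus: "The *Lifetime* version will be conducted during the screening visit". A since-last-contact version follows at all other visits. A yes "response to any C-SSRS category will be assigned a score as below": 1 to 5 for ideation, 6 to 10 for behavior, and 0 if nothing qualifies. The baseline rule is: "The baseline is defined as the most severe/maximum C-SSRS score at either screening or Week 0". The change display is "A shift table for change in C-SSRS categories of no suicidal ideation or behavior, suicidal ideation, and suicidal behavior from baseline through Week 16", repeated through Week 56 for the combined studies and from Week 16 to Week 56 for the extension, "where the baseline category is based on C-SSRS score form study 77242113PSO2001 and the post baseline is based on C-SSRS or AE data".

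The protocol describes the instrument differently. Section 8.2.7 and the Schedule of Activities name a Baseline/Screening version at screening and a Since Last Visit version from Week 0, and Section 8.2.7 calls the scale investigator-administered. The SAP calls it a participant self-report, then says site staff interview the participant. The screening form in protocol Appendix 7a carries the title note "Past x months = Past 6 months" and records ideation both over the lifetime and over the recent period. Exclusion criterion 19 applies to a candidate who "Has suicidal ideation or suicidal behavior in the last 6 months", subject to a risk assessment. SAP Appendix 2 declares no changes from the protocol-planned analyses.

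**The concern.** A shift table is meant to show who got worse relative to their state at entry. If the entry state is the worst point in a lifetime, a participant who had an episode years ago and none since starts in the ideation or behavior category, although nothing recent was present. If ideation then appears on treatment, the table shows no change or a move in the favorable direction. The shift tables are the only planned C-SSRS displays set against baseline, and the distortion falls on participants with a prior history. Because the extension tables take their baseline from the originating study, the same classification is carried through Week 56.

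**Working it through.** The documents give no planned figure for the C-SSRS, so there is nothing to reproduce. The check is of the category logic.

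**Inputs (SAP Section 5.6.3.3).** Scores run from 0 to 10. Write c(s) for the shift category of score s: c = 0 (none) if s = 0, c = 1 (ideation) if s is 1 to 5, c = 2 (behavior) if s is 6 to 10. Baseline B = max(screening score, Week 0 score). A participant worsens if c(post-baseline maximum) > c(B).

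**Step 1: which screening score.** Under the SAP's version name, the screening score covers the lifetime. Adopting the protocol's version name does not settle it, because that form also has a lifetime column and the SAP does not restrict the maximum to the recent one. Adding Week 0 can only raise B.

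**Step 2: who can be affected.** Exclusion 19 and protocol Section 8.2.7 judge screening ratings over the last 6 months. History older than that does not exclude under this criterion. Such a participant has B of 1 to 9 (a score of 10 is completed suicide and cannot be a baseline).

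**Step 3: all score pairs.**

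| Baseline | On-study maximum | Pairs | Worse | Same | Apparently better |
|---|---|---|---|---|---|
| Lifetime ideation, 1–5 | Ideation, 1–5 | 5 × 5 = 25 | 0 | 25 | 0 |
| Lifetime behavior, 6–9 | Ideation, 1–5 | 4 × 5 = 20 | 0 | 0 | 20 |
| Lifetime behavior, 6–9 | Behavior, 6–10 | 4 × 5 = 20 | 0 | 20 | 0 |
| Lifetime ideation, 1–5 | Behavior, 6–10 | 5 × 5 = 25 | 25 | 0 | 0 |
| Recent-window baseline of 0 | Ideation, 1–5 | 1 × 5 = 5 | 5 | 0 | 0 |

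The first two rows give 25 + 20 = 45 pairs with on-study ideation after a history: 0 worsen, 25 are unchanged and 20 look better. The last row is the same participant, with remote history only, under a recent-window baseline: all 5 ideation scores count as a worsening.

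**Step 4: what the counts mean.** They are counts of possible score combinations, not of participants or probabilities. In 10 of the 25 ideation-to-ideation pairs the score itself rises (for example 1 to 5) without a category change. That follows from using three broad categories and would remain after the baseline is corrected.

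**The case against.** The strongest reply is that nothing is lost from the report. Every cell of a shift table is printed, so on-study ideation after past behavior is there to be read in its own cell. SAP Section 5.6.3.3 also plans a summary of the most severe post-baseline C-SSRS outcome or adverse event, and a frequency distribution of the post-baseline maximum by intervention group. Section 5.6.2 adds a listing of participants with suicidal ideation or behavior. Protocol Section 8.2.7 sends new or worsening findings that the investigator judges clinically significant to the adverse event form. The arms are randomized, so an excess on drug could be seen in the post-baseline tables without any baseline. All of this stands, and it limits the point to how change from baseline is classified.

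A reader might infer that the plan conceals emergent suicidality, or that a calculable share of cases would go missing. The documents support neither. The cases are misclassified as not worsened rather than omitted, a move from ideation-only history to behavior still shows as worsening, and no prevalence of past history or event rate is given from which to work out a share.

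It can also be said that the worst-ever baseline is only one reading, since the protocol ties the screening rating to the last 6 months. That is fair as a guess at intent. But the SAP names a Lifetime version, scores any yes and takes the maximum, so a programmer following it would arrive at the lifetime value.

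**Conclusion.** Wrong as written, and minor: this is a descriptive safety output with no formal comparison and no bearing on the primary endpoint. On the SAP's wording, a participant whose only scored history is remote cannot be shown as worsening when ideation appears on study, and new behavior after lifetime behavior shows as no change. The error is confined to the baseline comparison in the shift tables, for the main study and the extension.

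The conclusion rests on two conditions: that the screening score feeding the maximum is the lifetime one, which the SAP implies and nowhere restricts, and that some participants with older history are enrolled, which the eligibility criterion permits. History means scored ideation or behavior; non-suicidal self-injury is not on the 0 to 10 scale. The number of participants affected cannot be computed from the documents.

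**What to change.** In SAP Section 5.6.3.3, state that the shift-table baseline is the worse of the recent-window screening score and the Week 0 since-last-visit score.

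- **Ideation:** use the past-6-months column, which the protocol form provides.
- **Behavior:** confirm which window was captured, then state it. The recent behavior column in Appendix 7a is headed in years with the number left blank, so a 6-month behavior baseline is not clearly collected, despite the appendix title.
- **Lifetime history:** show it as a separate row or stratum.
- **Consistency:** reconcile the version names and the mode of administration with protocol Section 8.2.7.
- **Extension:** apply the same baseline definition to the shift tables through Week 56.

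Participants with scored history inside the recent window who were judged not at risk, and so enrolled, would keep a non-zero baseline, as they should.

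The cost is a wording change, a small amount of extra tabulation and one check of the captured behavior window. For ideation no new data are needed.

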5.7. Other Analyses

5.7.1. Pharmacokinetics

5.7.1.1. JNJ-77242113 Concentrations

The PK evaluable population is defined as all the participants who received at least 1 complete dose of JNJ-77242113 and had at least 1 valid blood sample drawn for PK analysis after their first dose of JNJ-77242113.

Plasma JNJ-77242113 concentrations will be summarized by visit and treatment group. Plasma, concentration will be summarized using descriptive statistics (i.e., n, arithmetic mean, standard deviation [SD], coefficient of variation [%CV], median, range [minimum and maximum], and interquartile [IQ] range) at each visit. PK data may be displayed graphically.

The following analyses will be performed as appropriate.

- Summary of plasma JNJ-77242113 concentration over time
- Proportion of participants with plasma JNJ-77242113 concentration below the lowest quantifiable concentration in a sample at each visit
- Summary of plasma JNJ-77242113 concentrations over time by baseline body weight (≤ 90 kg, > 90 kg). Other covariates may also be applied
- Plots of median plasma JNJ-77242113 concentrations over time
- Plots of median plasma JNJ-77242113 concentrations over time by baseline body weight (\leq median, $>$ median)

Concentrations below the lowest quantifiable concentration will be treated as zero in the summary statistics. All plasma concentrations below the lowest quantifiable concentration or missing data will be labeled as such in the concentration database. PK data may also be displayed graphically.

If feasible, population PK analysis of plasma concentration-time data of JNJ-77242113 may be performed using nonlinear mixed-effects modeling. Data may be combined with those of other selected studies to support a relevant structural model. Available baseline participant characteristics (eg, demographics, laboratory variables, genotypes, race) will be tested as potential covariates affecting PK parameters. Details will be given in a population PK analysis plan and the results of the population PK analysis will be presented in a separate report.

77242113PSO2001

For study 77242113PSO2001, PK analysis set (Section 4.1) will be used and the analyses will be summarized through Week 16.

For the analyses, a participants included in one and only one treatment group on the basis of the treatment regimen followed. The description of treatment groups is as follows:

- JNJ-77242113 25 mg QD
- JNJ-77242113 50 mg QD
- JNJ-77242113 25 mg BID
- JNJ-77242113 100 mg QD
- JNJ-77242113 100 mg BID

77242113PSO2002

For study 77242113PSO2002, PK analysis set (Section 4.2) will be used and the analyses will be summarized through Week 52 (Week 36 of the study 77242113PSO2002).

- Placebo → JNJ-77242113 100 mg QD
- JNJ-77242113 25 mg QD
- JNJ-77242113 50 mg QD
- JNJ-77242113 25 mg BID
- JNJ-77242113 100 mg QD
- JNJ-77242113 100 mg BID

5.7.1.2. Data Handling Rules

Unless otherwise specified, the following data handling rules will apply to PK sample analyses:

[figure not shown]
- Plasma concentration summaries will be based on the actual treatment received.
- All plasma concentration summaries for a particular timepoint will include data obtained from treated participants at the timepoint of interest without imputing any missing data.
- A concentration not quantifiable (below the lower limit of quantification) will be treated as 0 in the summary statistics and shown as the lower limit of quantification (< LLOQ) in the data listings.
- The data from a participant who discontinued study agent will be excluded from the by-visit data analyses from that point onwards. In addition, the data from a participant who received an incomplete/ incorrect or skipped dose(s) based on 2 previous doses prior to the PK sample collection or data from a participant who skip dose prior to PK sample collection will be excluded for that visit.

5.7.1.3. PK vs Efficacy

To explore the relationship between JNJ-77242113 plasma concentrations and efficacy endpoints, the following analyses may be explored:

- The relationship between JNJ-77242113 plasma trough concentrations (quartiles) and PASI /IGA responses at Week 16 may be explored for study 77242113PSO2001.
- The relationship between JNJ-77242113 plasma trough concentrations (quartiles) and PASI /IGA responses at Week 52 (Week 36 of study 77242113PSO2002) may be explored for study 77242113PSO2002.

CCI

CCI

5.7.3. Pharmacokinetic/Pharmacodynamic Relationships

If data permit, the relationship between plasma concentration of JNJ-77242113 and PD (IL-23 mediated interferon-gamma production) may be analyzed graphically. If deemed necessary, a previously developed PK/PD model may be updated to describe the exposure-response relationship. If this is performed, details will be given in a population PK/PD analysis plan and results of the population PK/PD analysis will be presented in a separate technical report.

5.7.4. Biomarkers

Planned biomarker analyses may be deferred if emerging study data show no likelihood of providing useful scientific information.

Change in biomarkers over time will be summarized by treatment group. Associations between baseline levels and changes from baseline in select markers and response to treatment will be explored. The analyses will aim to identify biomarker relevant to treatment. These analyses are considered exploratory and will be summarized in a separate technical report.

5.7.5. Definition of Subgroups

To evaluate the consistency of the primary efficacy endpoint PASI75 response at Week 16, subgroup analyses may be performed in study 77242113PSO2001 when the number of participants in the subset permits

For each of the subgroups defined below, the difference between the JNJ-77242113 treatment groups and placebo group in the proportion of the PASI 75 responders at Week 16, the proportion of subjects achieving IGA score of cleared (0) or minimal (1), and its exact confidence intervals

will be calculated. No p-values will be provided. Subgroup analyses will not be stratified by weight category (≤ 90 kg, > 90 kg).

Demographic subgroups

Subgroup	Variant	Definition
Region	1	Define based on UN guidance as per the M49 standard 
 • Asian Pacific • North America • Europe
Sex	1	
 • male • female
Race	1	
 • American Indian or Alaska Native • Asian • Black or African American • White • Other
Age Group	1	
 • <45 • 45-64 • ≥ 65
BMI	1	
 • $<25 \text{ kg/m}^2$ • 25-$<30 \text{ kg/m}^2$ • $\geq 30 \text{ kg/m}^2$
Body Weight Group	1	
 • $\leq 90 \text{ kg}$ • $> 90 \text{ kg}$

Baseline disease characteristics and psoriasis medication subgroups

Subgroup	Variant	Definition
Age at diagnosis (years)	1	
 • $<$ median • \geq median
Psoriasis disease duration (years)	1	
 • $<$ median • \geq median
Baseline PASI	1	
 • <20 • ≥ 20
Baseline IGA	1	
 • < 4 • $= 4$
Baseline BSA	1	
 • $< 20\%$ • $\geq 20\%$
Baseline DLQI		
 • < 10 • ≥ 10
Psoriatic arthritis		
 • Yes • No
Topical agents (Topical non-corticosteroids, Topical corticosteroids)		
 • Never used • Ever used
Phototherapy (ultraviolet B light [UVB] or psoralen and ultraviolet A light therapy [PUVA])	1	
 • Never used • Ever used
Systemics (Conventional non-biologic systemics, Novel non-biologic systemics, 1,25-vitamin D3 and analog, phototherapy, biologics)		
 • Never used • Ever used

Subgroup	Variant	Definition
Conventional non-biologic systemics (PUVA, MTX, cyclosporine, acitretin, or Azathioprine)		
 Never used Ever used
Novel non-biologic systemics (apremilast, deucravacitinib, or tofacitinib)		
 Never used Ever used
Biologics (Etanercept, Infliximab, Adalimumab, Ustekinumab, Briakinumab, Secukinumab, Ixekizumab, Brodalumab, Guselkumab, Risankizumab, Tildrakizumab, Alefacept, Efalizumab, Natalizumab, Certolizumab pegol)		
 Never used Ever used
Anti-TNF α agent (etanercept, infliximab, Certolizumab pegol, or adalimumab)		
 Never used Ever used
IL-12/23 inhibitors (ustekinumab, briakinumab)		
 Never used Ever used
IL-17 inhibitors (secukinumab, ixekizumab, or brodalumab)		
 Never used Ever used

